2.1.5 Pharmacokinetic variables

Not applicable to the study.

2.1.6 Pharmacodynamic/genomics endpoints

Not applicable to the study.

2.1.7 Quality-of-life endpoints

Several patient-reported outcomes (PROs) endpoints will be evaluated using the following questionnaires: Diabetes Treatment Satisfaction Questionnaire Status (DTSQs) and Change (DTSQc) versions, MOS Sleep, and Work Productivity and Activity Impairment Questionnaire (WPAI).

Details on handling of missing data for PROs are available in Section 2.5.2.4.

2.1.7.1 DTSQs

The DTSQs is used to assess patient satisfaction with treatment and patient perception of blood glucose control; it is a validated questionnaire comprised of the 8 questions answered on a Likert scale from 0 to 6. It will be completed at baseline and Week 12.

Responses to questions 1, 4, 5, 6, 7, and 8 will be summed to produce a Total Treatment Satisfaction score ranging from 0 (no satisfaction) to 36 (high satisfaction with treatment).

The 2 items of 'perceived frequency of hyperglycemia' (question 2) and 'perceived frequency of hypoglycemia' (question 3) are scored separately ranging from 0 (none of the time) to 6 (most of the time).

2.1.7.2 DTSQc

The Diabetes Treatment Satisfaction Questionnaire Change Version (DTSQc) was developed from the original DTSQ to evaluate the change in treatment satisfaction at a specific time point. It contains 8 questions answered on a Likert scale from -3 to 3. The DTSQc instructions and response options differ from those of the DTSQs to produce measures of relative change in satisfaction rather than measures of absolute satisfaction. The DTSQc will be completed at Week 12.

Responses to questions 1, 4, 5, 6, 7, and 8 will be summed to produce a Total Treatment Satisfaction score ranging from -18 to 18. Positive scores are indicative of improvement in treatment satisfaction, whereas negative scores are indicative of deterioration in treatment satisfaction since start of the study.

The 2 items of 'perceived frequency of hyperglycemia' (question 2) and 'perceived frequency of hypoglycemia' (question 3) are scored separately ranging from -3 (much less of the time) to 3 (much more of the time), meaning negative scores indicate fewer problems with blood glucose levels and positive scores indicate more problems than before.

2.1.7.3 MOS Sleep

The MOS Sleep used to measure patient perception on key aspects of sleep, consisting of 12 questions that will be completed by the patients at baseline and Week 12. The MOS Sleep 12 items acute revised version with the 'past week' recall period will be used to collect information.

The 12-item MOS Sleep Scale assessment yields scores on six subscales: Sleep Disturbance (4-item subscale on sleep initiation problems, and sleep maintenance problems), Snoring (single-item subscale), Shortness of Breath or Headache (single-item subscale asking about the frequency of awakening with shortness of breath or with a headache), Sleep Adequacy (2-item subscale asking about frequency of awakening fresh and rested in the morning and getting the amount of sleep needed), Daily Somnolence (3-item subscale), and Sleep Quantity (single-item subscale representing the average number of hours slept).

The Sleep Problems Index is also calculated based on 9 of the items.

Responses to all but the open-ended sleep quantity item are transformed to scores on a 0-100 metric, with higher item scores reflecting more of the attribute implied by the scale name.

Scores on the multi-item subscales and indexes also range from 0 to 100.

MOS-sleep scores will be calculated automatically via the electronic system provided by the owner of this questionnaire.

2.1.7.4 WPAI

The WPAI SHP assesses the amount of absenteeism, presenteeism and daily activity impairment attributable to a specific health problem (WPAI:SHP version V2.0). An adapted version of the WPAI:SHP will be used with the term PROBLEM replaced by DIABETES, as requested by the author.

The WPAI:SPH consists of 6 questions which will be completed by the patients at baseline and Week 12.

The 6 questions will be used to derive 4 scores (see Section 2.5.2.4) and scores are multiplied by 100 to express in percentages.

2.1.8 Health economic endpoints

Not applicable to the study.

2.2 DISPOSITION OF PATIENTS

Screened patients are defined as any patients who signed the informed consent.

Randomized patients consist of all patients with a signed informed consent form who have been allocated a treatment kit based on a randomization process, regardless of whether the treatment kit was used.

Patient study status

For patient study status, the total number of patients in each of the following categories will be presented in the clinical study report using a flowchart diagram or summary table:

- Screened patients
- Screen failure patients and reasons for screen failure
- Treated but not randomized
- Randomized patients
- Randomized but not treated patients
- Randomized and treated patients
- Patients who completed the 12-week on-treatment period (patients who have performed Visit 18, who did not permanently discontinue)
- Patients who discontinued IMP by main reason for permanent treatment discontinuation
- Patients who did not complete the study
- Patients who discontinued the study by main reason for study discontinuation
- Status at last study contact (Alive/Death)
- Lost to follow-up

For all categories of patients (except for the screened and non-randomized categories) percentages will be calculated using the number of randomized patients as the denominator for each treatment group.

Reasons for treatment discontinuation will be supplied in tables giving numbers and percentages by treatment group.

Lost to follow-up will be based on the End of Study [EOS] page as 'Other' with specify 'Lost to Follow Up'.

All critical or major deviations potentially impacting efficacy analyses, randomization, and drug-dispensing irregularities, and other major or critical deviations will be summarized in tables giving numbers and percentages of deviations by treatment group.

Same summary as above will be displayed for any critical or major deviation due to COVID-19 pandemic. Patients excluded from Population without trial impact (disruption) due to COVID-19 will be listed.

The patients with any visit impacted by COVID-19 crisis will be summarized in a separate table giving numbers and percentages by treatment group.

Additionally, the analysis populations for safety and efficacy, will be summarized in a table by number of patients in the randomized population:

- Efficacy population: intent-to-treat (ITT) population, per-protocol population and Population without trial impact (disruption) due to COVID-19,
- Safety population.

2.2.1 Randomization and drug dispensing irregularities

Randomization and drug-dispensing irregularities occur whenever:

- A randomization is not in accordance with the protocol-defined randomization method, such as a) an ineligible patient is randomized, b) a patient is randomized based on an incorrect stratum, c) a patient is randomized twice, or d) in a dynamic randomization scheme the treatment assignment is, in fact, not random, due to a computer program error. OR
- A patient is dispensed an IMP kit not allocated by the protocol-defined randomization, such as a) a patient at any time in the study is dispensed a different treatment kit than as randomized (which may or may not contain the correct-as-randomized IMP), or b) a non-randomized patient is treated with IMP reserved for randomized patients.

Randomization and drug-dispensing irregularities will be monitored throughout the study and reviewed on an ongoing basis.

All randomization and drug-dispensing irregularities will be documented in the clinical study report. If the number of irregularities is large enough to make a tabular summary useful, the irregularities will be categorized and summarized among randomized patients (number and percentages). Nonrandomized, treated patients will be described separately.

Randomization and drug-dispensing irregularities to be prospectively identified as protocol deviations include but are not limited to:

- IMP dispensed without randomization,
- IMP dispensed prior to randomization,
- Patient randomized twice,
- IMP kit number actually dispensed to the patient is different from the IMP kit number allocated,
- Wrong stratum of randomization,
- IMP dispensed without allocation at re-supply visit,
- Non-existing patient randomized by error.

2.3 ANALYSIS POPULATIONS

Patients who are dispensed study drug without calling the IRT or before calling the IRT are considered non-randomized patients. They are excluded from any population for analysis, including safety.

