6.3 MEASURES TO MINIMIZE BIAS: RANDOMIZATION AND BLINDING

As Toujeo and the control drug Tresiba are distinguishable, this study is an open-label design, and no attempt will be made to blind the randomly assigned study treatment.

The Clinical Supplies Trial Supply Operations Manager will provide the treatment kit number list and the Study Biostatistician will provide the randomization scheme to the IRT. IRT will then generate the patient randomization list according to which it will allocate patients to either treatment arm.

The IMPs will be provided in open-label boxes and each type of kit is identified with a treatment number.

At the screening visit, the Investigator or designee will contact the IRT center to receive the patient number. This patient number is composed of a 12-digit number containing the 3-digit country code, 4-digit center code, and the 5-digit patient chronological number (which is 00001 for the first patient screened in a center, 00002 for the second patient screened in the same center, etc).

Patients can be re-screened once before randomization in case of non-eligibility or in cases where original screen failure was due to reasons expected to change at rescreening and based upon the Investigator's clinical judgment. Re-screened patients will be subject to the screening visit procedures/assessments including new informed consent signed and allocation of a new patient number.

Before randomization, baseline CGM results with accompanying CGM summary report certifying compliance with requirements MUST be available. In order for a patient to be randomized the baseline CGM performance (during Weeks -3 to -1) must reflect at least 10 days (not necessarily consecutive) of useable 24-hour CGM data (see Section 8.1.1.2 for the definition of useable data).

At Visit 6, only after patient eligibility is confirmed, the Investigator or designee will call the IRT for patient randomization and first treatment kit(s) allocation.

Only eligible patients will be randomized at a 1:1 ratio to receive Toujeo or Tresiba for 12 weeks. Randomization will be stratified by HbA1c at screening (<8.0%; $\ge8.0\%$).

A randomized patient is defined as a patient who is registered and assigned with a randomized treatment arm from the IRT, as documented from IRT log file, regardless of whether the treatment kit was used or not.

The IRT will be contacted at each time a treatment kit(s) allocation is necessary, ie, at Visit 6 (randomization) and also at Visit 14.

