9.3 POPULATIONS FOR ANALYSES

For purposes of analysis, the following populations are defined (Table 6):

Table 6 - Populations for analyses

Population	Description		
ITT	All randomized (patients who signed ICF and with a treatment arm allocated before first IMP and recorded in the IRT database) participants, irrespective of the treatment actually being received, analyzed according to the treatment group allocated by randomization.		
PP	The PP population is a subset of ITT population with no major protocol deviations. Participants included in this population will fulfill at least the criteria below:		
	 randomized and received only the treatment allocated at the randomization 		
	did not permanently discontinue treatment		
	The PP population will be fully defined in the SAP.		
Safety	All randomized participants who received at least one dose of IMP, regardless of the amount of treatment administered. Patients will be analyzed according to the treatment actually received.		

ICF: informed consent form; IRT: interactive response technology; ITT: intent to treat; PP: per protocol; SAP: statistical analysis plan

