2.3.1.1 Intent–to-treat population

The ITT population consists of all randomized patients, irrespective of the treatment received. Randomized patients are patients who signed the ICF and with a treatment group allocated before the first IMP administration and recorded in the IRT database.

Patients will be analyzed in the treatment group to which they are randomized.

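### SAP 2.3 goes by when study drug was dispensed and the ITT definition by when the IRT allocated, so a patient handed a kit before the IRT call but allocated before the first injection is both in and out of the ITT and safety populations

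*SAP*

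**What the plan says.** Four places in the documents say who counts as randomized, and a fifth attaches an exclusion.

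- **Protocol 6.3:** "A randomized patient is defined as a patient who is registered and assigned with a randomized treatment arm from the IRT". Use of the kit is irrelevant, and no timing condition relates to dispensing or injection.
- **Protocol 9.3, Table 6 (ITT):** all randomized participants "with a treatment arm allocated before first IMP and recorded in the IRT database".
- **SAP 2.3.1.1 (ITT):** "Randomized patients are patients who signed the ICF and with a treatment group allocated before the first IMP administration and recorded in the IRT database". This is the Table 6 rule.
- **SAP 2.2 (disposition):** consenting patients "who have been allocated a treatment kit based on a randomization process, regardless of whether the treatment kit was used".
- **SAP 2.3 (introduction to the populations):** "Patients who are dispensed study drug without calling the IRT or before calling the IRT are considered non-randomized patients". The next sentence reads "They are excluded from any population for analysis, including safety".

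SAP 2.3.2 builds the safety population from randomized patients with at least one full or partial dose. It adds that treated patients who were not randomized fall outside that population, with their safety data shown separately.

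SAP 2.2.1 lists dispensing irregularities to be recorded as protocol deviations. Dispensing without randomization and dispensing before randomization are two of them. A separate item is "IMP dispensed without allocation at re-supply visit".

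**The concern.** The SAP 2.3 sentence looks at the order of dispensing and the IRT call. The ITT definition looks at the order of IRT allocation and first administration. These are different pairs of events, so the two rules can classify the same patient differently. The SAP gives no order of precedence, and SAP 1.5, which lists changes to the protocol's statistical section, does not mention a narrower ITT or safety population.

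The primary analysis is on the ITT population. If SAP 2.3 is applied as written, a patient with a valid IRT allocation before the first dose leaves that analysis, including its multiple imputation, and also leaves the safety denominators. Table 6 promises the opposite.

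In this sequence the early handover comes before allocation, so the exclusion need not be related to arm. But the trial is open-label, and the order of two steps at one visit may be recorded or queried by staff who by then know the arm. Membership of the primary population should not turn on that.

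**Working it through.** **Step 1. Classify each possible sequence under each rule.**

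| Sequence | SAP 2.3 | Table 6 and SAP 2.3.1.1 | Protocol 6.3 |
|---|---|---|---|
| Dispensed and dosed, never entered in the IRT | Out | Out | Not randomized |
| Dispensed and injected, IRT allocation afterwards | Out | Out | Randomized |
| Kit handed over, then IRT allocation, then first injection | **Out** | **In** | Randomized |
| Randomized at Visit 6, re-supplied at Visit 14 without an IRT call | Out only if read literally | In | Randomized |

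The first row shows no conflict. In the second, the two ITT definitions and SAP 2.3 agree, and only protocol 6.3 differs because it has no timing condition. The third row is the direct contradiction.

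**Step 2. Can the third sequence occur?** Protocol 6.3 has the IRT contacted at Visit 6 for randomization and the first kit. Protocol 6.6.1.1 has the first injection that day under supervision, or the next morning if it could not be given at the site. There is therefore room for a kit to change hands before the call while the injection still follows allocation. SAP 2.2.1 foresees early dispensing by listing it as a deviation.

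**Step 3. Safety.** The third-row patient has an IRT allocation and a dose, so SAP 2.3.2 applied with the SAP 2.3.1.1 meaning of randomized puts the patient in the safety population. SAP 2.3 takes the patient out.

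**Step 4. Consistency with the per-protocol rules.** SAP 2.3.1.2 lists the deviations that remove a patient from PP, such as wrong treatment or wrong stratum. Early dispensing is not among them. An event not listed as grounds for leaving PP would, through SAP 2.3, remove the patient from ITT, of which PP is a subset.

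**Step 5. Size.** The documents give no rate for this irregularity. The plan's sample size, from protocol 9.2 and SAP 1.3, reproduces first:

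n = (1.96 + 1.282)² × 1.81 × 14.7² / (0.1 × 56)² = 131.09 per group, against 131 stated.

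Power = Φ(5.6 / [14.7 × √(1/n₁ + 0.81/n₀)] − 1.96), with n₁ for Toujeo and n₀ for Tresiba. At 131 per group this is 89.99%.

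Now assume, for illustration only, that some patients who would have been evaluable are lost from one arm:

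| Lost from one arm | Share of 338 | Power, lost from Toujeo | Power, lost from Tresiba |
|---|---|---|---|
| 1 | 0.3% | 89.9% | 89.9% |
| 2 | 0.6% | 89.7% | 89.8% |
| 5 | 1.5% | 89.4% | 89.5% |
| 10 | 3.0% | 88.7% | 88.9% |

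The largest assumed loss costs 1.1 to 1.3 percentage points.

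**The case against.** The case for leaving the text alone is that SAP 2.3.1.1 is the operative ITT definition, is explicit, and matches Table 6. On this view SAP 2.3 is a loosely worded introduction aimed at people who took drug outside the randomization system, and a kit handed over minutes before the call is a rare slip at one visit. No test, margin or sample size changes. The rarity and the small effect on power stand. The rest does not remove the contradiction: SAP 2.3 states a rule with a consequence for all populations, and nothing subordinates it to the section that follows.

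A reader might infer two stronger things that the documents do not support.

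- **That the plan expels properly randomized patients after 8 weeks for a re-supply error at Visit 14.** The sentence is not limited to first dispensing, so the literal words reach this patient. But SAP 2.2.1 lists unallocated re-supply separately from dispensing without or before randomization, and the SAP 2.3 wording parallels the latter two. SAP 2.2.1 also tabulates irregularities among randomized patients and describes non-randomized treated patients apart from them. The likely intent is first dispensing only, so this is an ambiguity to close and not an evident rule.
- **That these patients' safety data disappear.** SAP 2.3.2 presents them separately, SAP 2.4.5 lists safety data of exposed patients outside the safety population, and SAP 2.4.5.3 reports deaths in non-randomized patients. What is lost is their place in the denominators and in the comparison between arms.

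**Conclusion.** The contradiction is real for one defined patient: kit handed over before the IRT call, allocation recorded by the IRT, first injection after that. Table 6, SAP 2.3.1.1 and SAP 2.3.2 include that patient in ITT and safety; SAP 2.3 excludes the patient from both. Extension to Visit 14 re-supply is possible on the literal wording but probably not intended.

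The number affected cannot be taken from the documents. I expect it to be small, which is a judgement from the narrowness of the sequence and not a figure in the plan. Under the assumed losses above, power stays at or above 88.7%. The reason to act is that IRT-allocated patients could be left out of the primary analysis of an open-label trial under a rule that contradicts the protocol's population definitions.

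**What to change.** Replace the SAP 2.3 sentence with wording such as: *Patients who receive IMP without a treatment group having been allocated and recorded by the IRT before their first administration are treated as non-randomized.*

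Then add that patients allocated before first administration remain in ITT as randomized, and in the safety population if dosed. Early dispensing or re-supply without allocation should be handled as a deviation under SAP 2.2.1. This follows Table 6 and also settles, for the analysis, the sequence in which protocol 6.3 alone would count a patient dosed before allocation.

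The cost is one reworded sentence and one added statement in the SAP, made before database lock. A few irregular cases stay in the analysis and are already documented as deviations. No sample-size figure changes.

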2.3.1 Efficacy populations

The primary efficacy analysis population will be the ITT population.

2.3.1.1 Intent–to-treat population

The ITT population consists of all randomized patients, irrespective of the treatment received. Randomized patients are patients who signed the ICF and with a treatment group allocated before the first IMP administration and recorded in the IRT database.

Patients will be analyzed in the treatment group to which they are randomized.

2.3.1.2 Per-protocol population

The per-protocol population (PP) is a subset of the ITT population which will comprise all randomized patients, who are exposed, who do not permanently discontinued IMP allocated by IRT, who completed the study as per protocol (as reported in the EOS page) and who do not present any major protocol deviations that potentially impact the primary efficacy results, as presented below:

• Major or critical deviation linked to inclusion criteria:

- From inclusion criterion I02: Patients without T1DM.
- From inclusion criterion I03: Not treated with multiple daily injections (MDI) using basal insulin analog once daily and rapid acting insulin analogs for at least one year
- From inclusion criterion I04: HbA1c <7% or >10%
- Major or critical deviation linked to exclusion criteria:
 - With E09: Patients having received basal insulin dose ≥ 0.6 U/kg body weight within 30 days prior to screening.
 - With E13: Patients who will need real time, flash or implantable CGM for routine care any time during study participation.
 - With E23: Inappropriate CGM use during run-in period evidenced by failure to obtain a minimum of 10 days (not necessarily consecutive) of useable CGM data by the end of run-in.
- Other major or critical deviation potentially impacting primary efficacy results:
 - Not taken only the treatment allocated by IRT (ie, wrong treatment taken at randomization or switch during the study)
 - Wrong stratum of randomization
 - Taken any prohibited medications for more than 10 consecutive days during the study as follows:
 - Any glucose-lowering agents other than IMP, the patient's current background basal insulin analog during the run-in period (which may not be changed during the study), or the patient's existing mealtime insulin (which may not be changed during the study). This includes oral or injectable glucose lowering agents, other type of basal insulin (eg, NPH), pre-mixed insulin, and human regular insulin
 - Insulin pump therapy.
 - Systemic glucocorticoids (topical or inhaled applications are allowed).
 - Patient who did not receive the CGM at Week 9, or for whom there are issues with uploading the CGM data at Week 12. This will be evaluated for patients who completed the treatment period and the study

Of note: in case of CGM performed as planned in the protocol (20-days during Week 10, Week 11 and Week 12) but not evaluable (ie, less 10 days, [not necessarily consecutive] of useable CGM data among the 20-days of CGM), the patient is not excluded from PP population.

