4 STUDY DESIGN

4.1 OVERALL DESIGN

This is a multicenter, randomized, active-controlled, parallel-group, 12-week open-label study. The study consists of a 1- or 2-week screening period, followed by a 4-week run-in period, and a 12-week randomized treatment period.

During the first 2 weeks of the run-in period (Weeks -4 and -3), patients will undergo treatment stabilization of their current basal and mealtime insulin treatment, and will be trained and tested on how to perform study-related procedures. During the (-)3 – (-)1 weeks of run-in, patients will wear a CGM device, blinded both to patients and Investigators. This will be the baseline CGM period, when during 20 consecutive days, a minimum of (10 days, not necessarily consecutive) of useable CGM data must be generated, to be eligible for randomization.

Patients satisfying the study inclusion/exclusion criteria (including CGM performance requirements) will be randomized in a 1:1 ratio to morning injections of either Toujeo or Tresiba, which will replace the patient's current basal insulin.

An interactive response technology (IRT) will be configured and randomization will be stratified by HbA1c at screening (<8.0%; $\ge8.0\%$).

During the randomized treatment period, CGM data (blinded to both patients and Investigators) will be collected during Weeks 9-12 during 20 consecutive days.

The basal insulin injection will be once daily in the morning, defined as the time period between waking up and breakfast. The injection time will be discussed between the Investigators and patients at randomization and should be kept consistent at the same time each day.

During the entire study starting after the screening period, patients will perform SMPG as specified in the study flow chart. The SMPG readings will be used to guide insulin dose titration for optimal glycemic control.

Appropriate dose titration of basal and mealtime insulin will be implemented as described in the dose regimen section.

At the end of the study, the patients will be followed-up from 2 to 4 days after last IMP dose to collect posttreatment safety information.

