4.4 END OF STUDY DEFINITION

A participant is considered to have completed the study if he/she has completed all phases of the study including a 2 to 4 day follow-up period.

The end of the study is defined as the date of the "last patient last visit" planned with the protocol, including the follow-up visit.

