8.1.1.1 CGM performance

Two (2) sets of CGM will be conducted by the study patients. Baseline CGM will start at Visit 3 (Week -3) and stop at randomization visit (Visit 6). During the randomized treatment period, an endpoint CGM recording during Weeks 9, 10, 11 and 12 [Days 64 to 84]) will be done. Patients must be well trained to understand the importance of the CGM performance and compliance with the manufacture's (DexCom) instructions.

All patients will undergo training, delivered by the investigational site personnel, at Visit 2 regardless of previous experience with CGM. After the training, patients should understand the process of CGM and how to handle the CGM device at home, the distance of receiver and effect of temperature on the device etc. If the patient is not sufficiently compliant with the study procedures, all necessary training has to be repeated by the site staff.

Patients, Investigators, and study personnel will be blinded to the CGM data. The CGM receiver's screen will be blocked of displaying data. Neither patients nor Investigators will be able to see the glucose values.

At Visit 3 and Visit 15, the insertion of CGM sensor will occur under the supervision of Investigators or designees. Patients will be instructed to insert the sensor into the belly (abdomen) at least 8 cm (3 inches) away from the insulin injection sites.

After the CGM sensor being inserted, and the transmitter being attached, patients will stay in the study site as long as needed to explain the use of CGM. During the next 19 days when the patients are operating the CGM, they must:

- Carry the CGM receiver with them all the time; the receiver must be placed within 20 feet (6 meters) from the patients' body in order to capture the data measured by the device.
- After 10 days of wearing the device, patients must remove and replace the sensor themselves. **Note:** If required, Investigators can arrange for patients to attend the site after the first 10 days of CGM for the sensor to be replaced at the study site.

Patients will receive a user guide of instruction included in the DexCom G6 device kit. Technique support via a 24/7 help-line service for trouble shooting will be provided by the manufacturer, DexCom. The patients should immediately contact the sites if they encounter any device malfunction or device related events eg, sensor fracture. The Investigator or a site staff will help patients contact the DexCom service line for problem solving.

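### As worded, the per-protocol set drops patients who miss only the safety follow-up held after the primary endpoint has been recorded

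*SAP*

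**What the plan says.** SAP 2.3.1.2 builds the PP population from conditions that must all hold. The patient was exposed, did not permanently stop the allocated IMP, is one "who completed the study as per protocol (as reported in the EOS page"), and has no listed major deviation. The listed deviations are described as those that could affect the primary efficacy result. The last bullet, on CGM not received or not uploaded, is assessed only in patients who finished both the treatment period and the study.

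Protocol 4.4 defines study completion. A participant has completed when he or she has "completed all phases of the study including a 2 to 4 day follow-up period". Protocol 4.1 gives the purpose of that period: "the patients will be followed-up from 2 to 4 days after last IMP dose to collect posttreatment safety information".

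The Week 12 endpoint comes earlier. Protocol 8.1.1.1 schedules an "endpoint CGM recording during Weeks 9, 10, 11 and 12 [Days 64 to 84"].

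Protocol 9.3 (Table 6) lists minimum PP criteria, among them that the patient "did not permanently discontinue treatment", and adds: "The PP population will be fully defined in the SAP". Study completion is not among the listed minimum criteria.

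SAP 2.2 already has a disposition category that stops at Week 12: "Patients who completed the 12-week on-treatment period (patients who have performed Visit 18, who did not permanently discontinue"). Patients who did not complete the study are counted on a separate line.

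**The concern.** A per-protocol set should remove patients whose conduct could distort the endpoint. The completion condition reaches past the endpoint. By the time of the follow-up, the CGM has been worn, collected and uploaded, and treatment has ended. Missing that contact says nothing about time in range.

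At stake is the PP analysis, the first of three sensitivity analyses of the primary endpoint (SAP 2.4.4.1.2). In an open-label non-inferiority trial, readers look to it for support of the ITT result. A membership rule based on behaviour after the endpoint makes it harder to interpret, and it discards observed primary data with nothing gained in return.

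**Working it through.** The question is mainly one of wording, so the passages are set in time order and the definition is applied to a patient.

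**Timeline (protocol 1.3 and 8.1.1.1; SAP 2.5.4)**

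| Event | Study day |
|---|---|
| Endpoint CGM worn | 64 to 84 |
| Visit 18: CGM device collected, data uploaded | 84 |
| Visit 19: follow-up, 2 to 4 days after last dose | 86 to 88 |

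The SAP analysis window for the Week 12 CGM runs from Day 57 to Day 91. This allows for early or late recordings but does not make Visit 19 relevant, because the device is returned at Visit 18.

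**Applying SAP 2.3.1.2** to a patient who stays on the allocated insulin, wears the CGM as planned, attends Visit 18 and misses only Visit 19:

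1. Exposed: met.
2. No permanent discontinuation of IMP: met.
3. Study completed as the protocol defines it: not met, because protocol 4.4 includes the follow-up.
4. No listed major deviation: met. None of the listed deviations concerns a follow-up visit.

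The patient is out of the PP set on condition 3 alone and remains in the ITT population.

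**Could *study* be loose wording for the treatment period?** That is unlikely. SAP 2.2 reports completion of the on-treatment period and non-completion of the study as different lines. The last bullet of SAP 2.3.1.2 also names the two separately.

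**Size.** Neither document gives a rate of missed Visit 19, so only a range can be shown. Let x be the assumed share of PP patients with an observed Week 12 value who are lost for this reason alone, equal in both arms. The standard error then rises by about the factor 1/√(1 − x):

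- x = 2%: 1/√0.98 = 1.010, an increase of 1.0%
- x = 5%: 1/√0.95 = 1.026, an increase of 2.6%
- x = 10%: 1/√0.90 = 1.054, an increase of 5.4%

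**Why no power figure is attached.** The plan's sample size reproduces: (1.96 + 1.282)² × 1.81 × 14.7² / (0.1 × 56)² = 131.09, against 131 stated. That 131 is the number per arm with an evaluable Week 12 CGM for the primary comparison, which is decided on ITT. The PP set is defined differently, keeps some patients without an evaluable CGM, uses multiple imputation and has no power target. Power computed from 131 would not describe it.

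**The case against.** The strongest reply is that membership follows what the investigator records on the end-of-study page, which is not in the documents. If sites record completion at Visit 18, few or no patients would be lost. This stands as a limit on the size of the problem. It does not settle the wording, because the SAP ties completion to the protocol and the protocol's definition includes the follow-up.

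A reader might infer that the SAP contradicts protocol Table 6. It does not. Table 6 sets a floor and hands the full definition to the SAP, so adding a criterion is permitted. The criticism is that this criterion has no link to the endpoint.

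A reader might also see an inconsistency in keeping patients whose Week 12 CGM was performed but is not evaluable, while dropping one whose CGM is complete. A PP set selects on adherence and not on data availability, and retaining the former patients is a deliberate, stated choice. The contrast shows only that the completion rule can remove an observed endpoint.

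Finally, requiring study completion can be defended as a strict PP convention. However, the same section limits excluding deviations to those that could affect the primary efficacy result, and a missed safety contact after the last dose does not fit that principle.

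**Conclusion.** The point holds as a minor defect in the definition of one sensitivity population. Under the plain wording of SAP 2.3.1.2 and protocol 4.4, missing only the post-treatment follow-up removes a patient whose treatment and endpoint are complete. The effect on precision is small over the assumed range: the standard error rises by about 1% to 5% for a loss of 2% to 10%. It may be nil if the end-of-study page records completion at Visit 18.

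Two stronger readings are not supported. The primary conclusion and its 90% power are not weakened, because non-inferiority is judged on ITT, where these patients' CGM data remain. Nor is bias between arms shown. That would need missed follow-up to differ by arm and to be related to time in range, and the documents give no reason to expect either. What remains is an avoidable loss of observed data and a selection rule applied after the endpoint in the PP check.

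**What to change.** In SAP 2.3.1.2, replace the study-completion condition with *who performed Visit 18 (Week 12)*. Keep the separate condition of no permanent IMP discontinuation. Together these match the on-treatment completer category in SAP 2.2.

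In the last bullet of the same section, limit the CGM check to patients who *completed the treatment period (Visit 18)*. Otherwise study completion remains in the definition by another route.

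The cost is two short edits, best made before database lock. Visit 18 completion is already derived for the disposition table, so no new data are needed, and the sample size does not change. Patients who stop treatment early, or who leave before Week 12, remain excluded.
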